2. STUDY OBJECTIVES AND ENDPOINTS

Objectives:

The primary objective of this study is to determine if temporary androgen suppression induced by degarelix improves the clinical outcomes of Veterans who are hospitalized to an acute care ward due to COVID-19 as defined by a reduction in mortality, ongoing need for hospitalization, or requirement for mechanical ventilation/extracorporeal membrane oxygenation (ECMO).

The secondary objectives of this study are to determine if temporary androgen suppression induced by degarelix reduces time to the clinical improvement, inpatient mortality, length of hospitalization, duration of intubation for mechanical ventilation, time to achieve a normal temperature, or the maximum severity of COVID-19 illness.

Endpoints:

Primary Endpoint:

Determine if degarelix + best supportive care (BSC) as compared to placebo + BSC reduces the composite endpoint of mortality, need for ongoing hospitalization, or requirement for mechanical ventilation/extracorporeal membrane oxygenation (ECMO) at Day 15 after randomization.

Secondary Endpoints:

- Determine if degarelix + best supportive care (BSC) as compared to placebo + BSC reduces the composite endpoint of mortality, ongoing need for hospitalization, or requirement for mechanical ventilation/extracorporeal membrane oxygenation (ECMO) at Day 30 after randomization.
- Determine if degarelix + BSC as compared to placebo + BSC reduces time to the clinical improvement as defined by a decline of 2 categories or more from the baseline on the modified 7-category ordinal scale of clinical status of hospitalized influenza patients (influenza scale, see Appendix A)¹, or hospital discharge, whichever comes first.
- Determine if degarelix + BSC as compared to placebo + BSC reduces inpatient mortality.
- Determine if degarelix + BSC as compared to placebo + BSC shortens the duration of hospitalization.

- Determine if degarelix + BSC as compared to placebo + BSC shortens the duration of intubation for mechanical ventilation.
- Determine if degarelix + BSC as compared to placebo + BSC reduces the time to normalization of temperature ($T < 37.5^{\circ}\text{C}$ for ≥ 48 hours).
- Determine if degarelix + BSC as compared to placebo + BSC reduces the maximum severity of COVID-19 illness based on the influenza severity scale (see Appendix A).

Exploratory Endpoints

- Determine if age, use of angiotensin converting enzyme inhibitors, the duration of pre-hospitalization symptoms, or the presence or absence of hypertension, cardiovascular disease, asthma, diabetes mellitus, or COPD are predictive of clinical outcome defined by the primary endpoint or any secondary endpoint.
- Determine if baseline, Day 8 or Day 15 values for D-dimer, IL-6, LDH, ferritin, total WBC, absolute neutrophil count (ANC), absolute lymphocyte count (ALC), or testosterone are predictive of clinical outcome defined by the primary endpoint or any secondary endpoint.
- Determine if degarelix + BSC as compared to placebo + BSC reduces nasopharyngeal (NP) epithelial or peripheral blood mononuclear cell (PBMC) TMPRSS2 expression, NP and plasma viral load, or serum cytokine (TNF α , IL-1 β , IL-6) levels.
- Determine whether germline genomic factors are predictive of clinical outcome defined by the primary endpoint or any secondary endpoint. This analysis is optional and is contingent on obtaining adequate number of samples.
- To determine the temporal onset of anti-viral antibodies.

Definition of Need for Ongoing Hospitalization (i.e. discharged): Patients who no longer require hospitalization on an acute bed ward for COVID-19 or its complications will be considered discharged (i.e. do not need ongoing hospitalization). For example, if a patient does not require ongoing hospitalization on an acute care ward due to COVID-19 but has remained on a non-acute inpatient unit (e.g. physical rehabilitation unit), the patient will be considered discharged for the purpose of the endpoints of this study. However, if the patient has a major complication of the hospitalization for COVID-19 (e.g. stroke) and requires ongoing hospitalization for this complication in an acute care bed, then this the patient will be considered as hospitalized for the purpose of endpoint definition even if the COVID-19 itself is deemed to have been adequately treated (i.e. no ongoing signs and symptoms that are directly due to COVID-19).

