Secondary endpoints included in the data analysis are the composit endpoint at 30 days after randomization, time to clinical improvement, inpatient mortality, length of hospital stay, length of intubation for mechanical ventilation, time to normal temperature, and the maximum severity of COVID-19 illness, which are defined in the endpoint section. The secondary endpoint analyses will be adjusted for multiplicity with a α -level of 0.0071 for each endpoint.

The composite outcome of mortality, ongoing need for hospitalization, and ECMO or mechanical intubation at 30 days after randomization as a secondary endpoint will be analyzed using the methods described in the the primary endpoint analysis.

For the time to clinical improvement as defined by a decline of 2 categories or more from the baseline on the modified 7-category ordinal scale of clinical status of hospitalized influenza patients (influenza scale, see Appendix A) or hospital discharge (see section 2 for definition of discharge) whichever comes first, survival analysis techniques will be used to analyze the time-to-event data for this endpoint. Patients whose conditions getting worse or died or withdraw from the study without clinical improvement will be censored. Kaplan-Meier analysis will be used to compare the two curves of the time to the clinical improvement over the patient follow-up time between the two treatment groups and a log-rank statistic will be used to test the equality of the survival function estimates of the two treatment groups using SAS PROC LIFETEST. Kaplan-Meier curves will be created. Additional analysis will be conducted using the Cox's Proportional Hazards model to test the treatment efficacy of the treatment intervention on the time until endpoint events adjusted for three prognostic factors: age, hypertension, and COPD. The hazard ratio and 95% confidence interval (CI) will be presented using SAS PROC PHREG. If the coefficient for treatment effect is significant, then the null hypothesis will be rejected. The regression model will be checked for the model assumption, adequacy, and the goodness of fit. If the model shows lack of fit, then alternate models with assumptions that are better met by the study data will be considered.

For mortality endpoint data analysis, the treatment effect will be analyzed initially with a Pearson χ^2 test and logistic regression will also be performed using SAS PROC

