### 2.4.2 Secondary Outcome Variables

There are five secondary outcome measures

1. The composite endpoint of mortality, ongoing need for hospitalization, or requirement for mechanical ventilation/extracorporeal membrane oxygenation (ECMO) at 30 days after the randomization.
2. The time to clinical improvement as defined by a decline of 2 categories or more from the baseline on the modified 7-category ordinal scale of clinical status of hospitalized influenza patients (influenza scale, see Appendix 5.1) or hospital discharge, whichever comes first.
3. Inpatient mortality
4. Length of hospital stay
5. Duration of intubation for mechanical ventilation
6. Time to normal temperature (< 37.5°C for ≥ 48 hours)
7. The maximum severity of COVID-19 illness based on the influenza severity scale (see Appendix 5.1)

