#### **3.7.5 Long Term Effect Analysis**

The long-term analysis will be based on the data collected by following the randomized participants up to 60 days after randomization, which will include mortality, readmission to hospital, and oxygen use.

For mortality analysis, the treatment effect will be analyzed initially with a Pearson  $\chi^2$  test (Table 3.7.5.1a) and then logistic regression will be performed using SAS PROC LOGISTIC by taking account of prognostic factors described in the primary endpoint analysis (Table 3.7.5.1b).

For hospital readmission rate analysis, the treatment effect will be analyzed initially with a Pearson  $\chi^2$  test (Table 3.7.5.2a) and then logistic regression will be performed using SAS PROC LOGISTIC by taking account of prognostic factors described in the primary endpoint analysis (Table 3.7.5.2b). Further, time to hospital readmission will also be analyzed based on survival analysis techniques using log-rank test and Kaplan-Meier curves (Figure 3.7.5.1) by PROC LIFETEST, and Cox regression model adjusted for the covariates as described in the secondary endpoint analyses (Tables 3.7.5.3a-b).

For the oxygen use analysis, Pearson  $\chi^2$  test will be performed for this categorical endpoint using SAS PROC FREQ initially. Given the endpoint is also an ordinal variable, Cochran-Armitage test will be performed to test the ordinal trend

tendency using SAS PROC FREQ (Table 3.7.5.4a). in addition to the frequency analysis, proportional odds logistic regression will also be performed (Table 3.7.5.4b) using SAS PROC LOGISTIC by taking account of the factors of age, hypertension, COPD, and the baseline influenza scale (see Appendix 5.1).

The long-term analyses will not be adjusted for multiplicity.

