## Appendix 5.2 Study Flow

### Appendix 5.3.1 Data Collection Schema

### Appendix 5.3.2 Data Collection Schedule

Form #	Form Name	Visit 00 (Screening / Baseline)	Visit 01 (Randomization / Day 1)	Visit 01 (Assessments 02-07)	Visit 02 (Day 8)	Visit 02 (Assessments 02-07)	Visit 03 (Day 15)	Visit 03 (Assessments 02-07)	Visit 04 (Day 22)	Visit 04 (Assessments 02-07)	Visit 05 (Day 30)	Visit 06 (Day 37)	Visit 07 (Day 44)	Visit 08 (Day 51)	Visit 09 (Day 60)	Visit 10-17 (if patient is still hospitalized complete weekly until discharge)
1	Screening and Randomization	R														
2	Demographics	R														
3	Medical History	R														
4	Baseline Medical Status	R														
5	Study Treatment		R													
6	Concomitant Medication Log	A	A	A	A	A	A	A	A	A	A	A	A	A	A	A
7	Medical Status				R		RH		RH		RH	RH	RH	RH	RH	RH
8	Laboratory Measures	R	R		R		RH		RH		RH					
9	Ordinal Scale of Clinical Status**	R	R	A	R	A	RH	A	RH	A	RH	RH	RH	RH	RH	RH
10	Protocol Deviation	A	A	A	A	A	A	A	A	A	A	A	A	A	A	A
11	Adverse Event	A	A	A	A	A	A	A	A	A	A	A	A	A	A	A
12	AE Follow-up	A	A	A	A	A	A	A	A	A	A	A	A	A	A	A
13	Serious Adverse Event	A	A	A	A	A	A	A	A	A	A	A	A	A	A	A
14	SAE Follow-up	A	A	A	A	A	A	A	A	A	A	A	A	A	A	A
15	Participant Termination		A	A	A	A	A	A	A	A	A	A	A	A	A	A
16	Research Blood and Nasal Swab Collection (GLA)										RH					
17	Total Testosterone Measurement (CSP completion)										R					
18	Post Discharge Follow-up										RD				RD	

R = Required

RH=Required if patient is still hospitalized (i.e. until discharge is noted on Form 07).

RD=Required if patient was discharged

A = As needed

\*\*Ordinal Scale of Clinical Status will be completed at screening, day 1 and whenever a status change occurs in the patient, but no less than 1x week.

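### The only stand-alone mortality test at the 0.0071 level counts inpatient deaths with no fixed day, so earlier discharge on degarelix would bias it in the drug's favour.

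*Protocol*

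**What the plan says.** **Mortality endpoint.** Protocol section 2 sets the aim: "Determine if degarelix + BSC as compared to placebo + BSC reduces inpatient mortality". SAP 2.4.2 repeats it as inpatient mortality. Neither gives a day. Protocol section 10 and SAP 3.7.2 test each secondary endpoint at a "level of 0.0071 for each endpoint".

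**Discharge as a target.** A separate secondary endpoint reads: "Determine if degarelix + BSC as compared to placebo + BSC shortens the duration of hospitalization". Remaining in hospital is also a component of the primary composite, and discharge counts as an event in time to clinical improvement. Under the protocol's definition, a man who no longer needs an acute bed but stays on a non-acute inpatient unit is out of hospital: "the patient will be considered discharged for the purpose of the endpoints of this study".

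**Follow-up after discharge.** Protocol section 5 follows men to death or Day 60. Footnote J of the Schedule of Events collects vital status and re-hospitalisation after discharge. In SAP Appendix 5.3.2 the post-discharge form (Form 18) is required for discharged men, in columns that read as Days 30 and 60. SAP 3.7.5 uses these data for a 60-day mortality comparison, but "The long-term analyses will not be adjusted for multiplicity". SAP 2.3, by contrast, ends follow-up at death or discharge.

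**Maximum severity.** SAP 2.4.2 lists "The maximum severity of COVID-19 illness based on the influenza severity scale" and gives no observation window.

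**The concern.** Discharge happens after randomisation, and the treatment is meant to change when it happens. An endpoint that stops counting at discharge therefore watches the two arms for different lengths of time if the drug works as hoped on length of stay. Suppose degarelix sends men home sooner and leaves total deaths unchanged. More degarelix deaths then fall after discharge and drop out of the inpatient count.

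This matters because inpatient mortality is the only mortality-only comparison in the family that shares the secondary alpha. A reader of the results would take it as the trial's controlled evidence on death. The data for a comparison without this cut-off are already planned, but the controlled test does not use them.

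**Working it through.** **1. The plan's alpha.** Seven secondary endpoints sharing 0.05 gives 0.05/7 = 0.00714, which rounds to the stated 0.0071.

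**2. Direction.** The planning rates for the Day 15 composite are 60% on placebo and 35% on degarelix (Protocol section 10). The complement is the share of men alive and out of acute care at Day 15: 1 − 0.60 = 40% and 1 − 0.35 = 65%. The plan thus expects earlier discharge on degarelix. This gives the direction only, because it describes timing at one day and the mortality endpoint has no day.

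**3. Size under assumptions.** Let m be true mortality, equal in both arms, and s the share of deaths that fall after discharge.
- Inpatient mortality = m(1 − s).
- Apparent risk ratio = (1 − s on degarelix)/(1 − s on placebo), which does not depend on m.
- m = 17% is the two-week BSC mortality cited in Protocol section 10. The values of s are assumptions.

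For the chance of a false benefit, n is 66 on placebo and 132 on degarelix, and the two-sided critical value at 0.0071 is about 2.69. The probability is 1 − Φ[(2.69 × SE0 − d)/SE1]. Here d is the difference in inpatient mortality, SE0 the pooled standard error and SE1 the unpooled one.

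Worked case, s = 10% and 20%:
- Inpatient mortality is 0.17 × 0.90 = 15.3% on placebo and 0.17 × 0.80 = 13.6% on degarelix, so d = 0.017.
- The pooled rate is (66 × 0.153 + 132 × 0.136)/198 = 0.1417.
- SE0 = 0.0526 and SE1 = 0.0534.
- (2.69 × 0.0526 − 0.017)/0.0534 = 2.33, which gives 1.0%.

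| s, placebo / degarelix | Inpatient mortality, placebo / degarelix | Apparent RR (true 1.00) | False benefit at 0.0071 |
|---|---|---|---|
| 10% / 10% | 15.3% / 15.3% | 1.00 | 0.36% |
| 10% / 20% | 15.3% / 13.6% | 0.89 | 1.0% |
| 10% / 30% | 15.3% / 11.9% | 0.78 | 2.5% |
| 20% / 40% | 13.6% / 10.2% | 0.75 | 2.9% |

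With true mortality between 10% and 25%, the three rows with unequal shares give 0.8% to 4.1%. The first row shows that post-discharge deaths alone do no harm to the ratio; the bias needs a larger share on degarelix.

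**4. Power.** For a true fall in mortality of 42%, from 17% to 0.17 × 0.58 = 9.9%, power at 0.0071 with 66 and 132 men is about 12%. The practical product of this endpoint is therefore its estimate, and that is where the bias acts.

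**5. Maximum severity, passages side by side.** Footnote C of the protocol's schedule continues the ordinal scale while the man is in hospital. In SAP Appendix 5.3.2 the scale form (Form 09) carries this code from Day 15: "RH=Required if patient is still hospitalized (i.e. until discharge is noted on Form 07". The note under the same table asks for the form at any change in status, with no hospital condition. Level 7 of the scale is death, wherever it occurs. The first two suggest a stop at discharge and the last two do not, so the window is undefined.

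**The case against.** The other side has good points, and several of them limit the finding.

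- **Mortality without the cut-off is already analysed.** SAP 3.7.5 compares 60-day mortality in the randomised men. A reader might infer that the trial could not tell fewer deaths from fewer observed deaths. That is not supported: the 60-day analysis can do so, although without alpha control.
- **The Day 30 composite counts any death.** It is tested at 0.0071 and is not limited to inpatient deaths. But it mixes death with remaining in hospital, so it cannot show whether deaths fell.
- **The edges of inpatient death are not defined.** Nothing confines it to the index admission, so a death on readmission might count, which would shrink the bias. Whether a death on a non-acute unit counts is also unstated. A worked patient history that scores such men one way would assume rules the documents do not contain.
- **The effect is small against the noise.** At 17% mortality the standard error of the difference is √(0.17 × 0.83 × (1/66 + 1/132)) = 5.7 points, and significance needs about 2.69 × 5.7 = 15 points. This stands, and it is why the point concerns the estimate more than the test.
- **It is a consistent design choice in a phase 2 trial.** That is true of the endpoint's name. It does not explain why the controlled mortality test should depend on when a man is discharged.

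**Conclusion.** The point holds for mortality. The only mortality-only test at 0.0071 stops counting at discharge, and if degarelix speeds discharge without changing deaths, the comparison is biased in its favour. The apparent risk ratio is 0.89 to 0.78 if 10% of placebo deaths and 20% to 30% of degarelix deaths follow discharge, with 17% true mortality in both arms. The chance of a false-positive finding is then about 1.0% to 2.5%. These shares are assumptions; the documents fix the direction but not the size.

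Two ways of getting a firmer number are tempting. The first multiplies the 25-point Day 15 discharge gap by an assumed post-discharge death rate. That applies a Day 15 gap to an endpoint with no day and gives no later deaths to men discharged after Day 15. The second is a constant-hazard model fitted to the planning rates, with the death hazard unchanged by discharge. It gives an inpatient risk ratio of 0.65 at Day 30 while the all-cause ratio is 1.00, but it also implies 39.6% all-cause mortality by Day 30. It is an extreme case that shows direction only.

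For maximum severity, a reader might infer that observation stops at discharge. The documents do not settle that. What stands is a minor consistency point: no window is stated and the form instructions conflict.

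**What to change.** 1. In Protocol section 2 and SAP 2.4.2, 3.7.2 and Appendix 5.6, replace inpatient mortality with all-cause mortality through Day 30 in all randomised men, taken from Forms 09, 15 and 18. Report inpatient death descriptively. State how a man with unknown vital status at Day 30 is handled.
2. Reconcile SAP 2.3, which ends follow-up at death or discharge, with the protocol's follow-up to Day 60.
3. Define maximum severity as the worst category from randomisation through Day 30, with any death scored 7, and make footnote C, the Form 09 code and the table note agree with that.

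**Cost.** The swap is one for one, so seven endpoints remain, alpha stays at 0.05/7 = 0.0071 and the sample size stays at 198. Vital status after discharge is already collected. The downside is that a few post-discharge deaths unrelated to COVID-19 will be counted. Scoring severity after readmission may also need a records check for care outside the VA.

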^H Collection of research blood and NP swabs will be attempted at the indicated time points, but it is understood that some of these samples may not be obtained due to logistical reasons, such as safety. Accordingly, the failure to collect the research blood or NP swabs will not be considered a protocol deviation.

^I EKG. EKGs beyond the screening window will be performed per standard of care.

^J Upon discharge, patients will be followed for vital status, need for re-hospitalization, and adverse events.

^K Inflammatory blood tests = CRP, IL-6, ferritin and pro-calcitonin.

Laboratory abnormalities observed during study enrollment will be managed according to local hospital practices and good standard of care. Study teams will focus on electrolyte abnormalities that could impact risk for cardiac events.

Handling of Research Specimens

The research specimens will be transported to UCLA for analysis on the same day of collection whenever possible. If samples cannot be transported to UCLA on the same day of collection, then the samples will be stored within the GLA Medical Center Building 500 Clinical Research Center. In the Clinical Research Center, the NP swabs will be stored at room temperature, and blood specimens will be stored at -20°C.

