11. DATA COLLECTION AND QUALITY ASSURANCE

Data Collection Forms

Data will be collected for each patient as described in the Table of Schedule of Events. Electronic case report forms (eCRFs) will be completed for screening, Days 1, 8, 15, 22, and 30 and then weekly until discharge (discharge being defined as no longer requiring hospitalization for COVID-19) or death.

Data Management

Access to individual identifiable patient information will be available to the PI, the co-PIs, and study staff. eCRFs will be generated to track clinical, laboratory, and radiographic data. Each study site will maintain records for its patients. Each site will have access only to data entered at its respective site. Investigators will not have access to unblinded study data.

The Perry Point CSPCC will serve as the Data Coordinating Center for this trial. Data collection will be accomplished using the Clinical Data Management System (CDMS), *iDataFax*, licensed by DF/Net. *iDataFax* is a hybrid data management system that can collect data from both paper and electronic sources, as well as allow for direct data entry. Direct data entry will be permitted in this study. Data will be entered from corresponding source documentation and from paper case report forms (CRFs) designed for this trial. Patient medical records and case report forms will serve as the original sources of data for verification. Data from these sources will be entered and submitted and after submission will be reviewed by Perry Point Clinical Data Managers. The end users will access the CDMS with credentials issued to them from the Perry Point CSPCC; these credentials are dependent on their roles at the site and on their completion of required data management, privacy protection, human subjects protection (HSP), and good clinical practices (GCP) training.

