### **3.7.2 Secondary Endpoint Analyses**

Secondary endpoints included in the data analysis are the composite outcome of mortality, ongoing need for hospitalization, and ECMO or mechanical intubation at 30 days after randomization, time to clinical improvement, inpatient mortality, length of hospital stay, length of intubation for mechanical ventilation, time to normal temperature, and the maximum severity of COVID-19 illness, which are defined in the endpoint section. The secondary endpoint analyses will be adjusted for multiplicity with a  $\alpha$ -level of 0.0071 for each endpoint.

The composite outcome of mortality, ongoing need for hospitalization, and ECMO or mechanical intubation at 30 days after randomization as a secondary endpoint will be analyzed using the methods described in the primary endpoint analysis (Tables 3.7.2.1a-c).

For the time to clinical improvement as defined by a decline of 2 categories or more from the baseline on the modified 7-category ordinal scale of clinical status of

hospitalized influenza patients (influenza scale, see Appendix 5.1) or hospital discharge (see section 2 for definition of discharge) whichever comes first, survival analysis techniques will be used to analyze the time-to-event data for this endpoint. Participants whose condition worsened, who died, or who withdrew from the study without clinical improvement will be censored. Kaplan-Meier analysis will be used to compare the two curves of the time to the clinical improvement over the patient follow-up time between the two treatment groups and a log-rank statistic will be used to test the equality of the survival function estimates of the two treatment groups using SAS PROC LIFETEST. Kaplan-Meier curves will be created (Figure 3.7.2.1). Additional analysis will be conducted using the Cox's Proportional Hazards model to test the treatment efficacy of the treatment on the time until endpoint events adjusted for three prognostic factors: age, hypertension, and COPD. The hazard ratio and 95% confidence interval (CI) will be presented using SAS PROC PHREG (Table 3.7.2.2). If the coefficient for treatment effect is significant, then the null hypothesis will be rejected. The regression model will be checked for the model assumption, adequacy, and the goodness of fit. If the model shows lack of fit, then alternate models with assumptions that are better met by the study data will be considered.

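### Read literally, the discharge definition scores a live transfer to hospice for COVID-19 as a favourable outcome, and the only alpha-controlled stand-alone mortality endpoint stops counting at discharge

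*Protocol*

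**What the plan says.** Protocol section 2 defines discharge by need for acute care: "Patients who no longer require hospitalization on an acute bed ward for COVID-19 or its complications will be considered discharged". A man who stays on a non-acute inpatient unit falls under the rule: "the patient will be considered discharged for the purpose of the endpoints of this study". A rehabilitation unit is the only example. The one exception keeps as hospitalised a patient who still needs an acute bed for a major complication. Neither document mentions hospice, comfort care or withdrawal of care. Protocol section 11 words discharge differently, as "discharge being defined as no longer requiring hospitalization for COVID-19", without the complications.

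The endpoints use this definition as follows.

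- **Primary endpoint:** the "composite endpoint of mortality, need for ongoing hospitalization, or requirement for mechanical ventilation/extracorporeal membrane oxygenation (ECMO) at Day 15 after randomization". Mortality is its own component and is not limited to deaths in hospital.
- **Time to clinical improvement:** a fall of at least two categories "or hospital discharge (see section 2 for definition of discharge) whichever comes first". Death is censored only when no improvement came first (SAP 3.7.2). The cross-reference works only for Protocol section 2, since SAP section 2 contains no such definition.
- **Inpatient mortality:** stated only as "Determine if degarelix + BSC as compared to placebo + BSC reduces inpatient mortality". Neither document defines inpatient.
- **Multiplicity:** each of the seven secondary endpoints is tested at 0.0071.

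On follow-up, footnote J to Protocol Table 1 says: "Upon discharge, patients will be followed for vital status, need for re-hospitalization, and adverse events". SAP Appendix 5.3.2 requires the post-discharge form (Form 18) at Day 30 and Day 60. Protocol section 5 follows patients to death or Day 60, and SAP 3.7.5 analyses mortality up to 60 days without multiplicity control. SAP 2.3, however, ends follow-up at death or discharge.

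**The concern.** A rule based on need for an acute bed cannot tell a man who has recovered from one whose acute treatment has ended because he is dying. Both stop needing the acute ward and both are discharged for every endpoint. The second man is then counted on the side of benefit for clinical improvement and length of stay, and for the primary endpoint if he is alive and unventilated on Day 15.

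The inpatient-mortality problem is wider and does not depend on hospice. If the observation window closes at discharge, and treatment is meant to bring discharge forward, the length of the window is itself affected by treatment. At stake is the one stand-alone mortality comparison for which the plan controls alpha.

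**Working it through.** **Scoring under the literal definition.** Take a man moved alive to hospice because of COVID-19 and not ventilated afterwards.

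| Endpoint | Dies by Day 15 | Dies Day 16 to 30 | Alive at Day 30 |
|---|---|---|---|
| Day 15 composite | Failure (death) | Non-failure | Non-failure |
| Day 30 composite | Failure (death) | Failure (death) | Non-failure |
| Time to improvement | Event no later than transfer date | Event no later than transfer date | Event no later than transfer date |
| Length of stay | Ends at transfer | Ends at transfer | Ends at transfer |
| Inpatient mortality, ordinary meaning | Not counted | Not counted | No death |
| 60-day mortality, SAP 3.7.5 | Counted | Counted | Counted if by Day 60 |

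The primary endpoint is exposed only to men transferred and still alive on Day 15. Clinical improvement and length of stay are exposed to every such transfer.

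**Reproducing the plan's sample size.** Inputs from Protocol section 10: p1 = 0.60 (placebo), p2 = 0.35 (degarelix), two-sided 0.05, 90% power, 2:1 allocation.

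- Pooled rate = (0.60 + 2 × 0.35)/3 = 0.4333.
- Placebo n = [1.96 × √(0.4333 × 0.5667 × 1.5) + 1.2816 × √(0.60 × 0.40 + 0.35 × 0.65/2)]² / 0.25² = (1.1895 + 0.7622)²/0.0625 = 60.9, so 61.
- Total = 61 + 122 = 183, against 186 stated (within 3%).
- Power with 62 and 124: SE under the null 0.0771, under the alternative 0.0755; Φ[(0.25 − 1.96 × 0.0771)/0.0755] = Φ(1.31) = 90.5%.

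**Sensitivity of the primary test.** Let h be the proportion transferred to hospice, alive and unventilated on Day 15, so that the observed failure rate falls by h. The documents give no value; 1% to 5% is an assumption (198 × 0.01 = 2 to 198 × 0.05 = 10 patients if it applies to both arms). The power formula is the one above, with 62 and 124 patients.

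| Assumed h | Both arms fall by h: power | Placebo only: power | Degarelix only, no true effect (60% in both): chance of a significant result favouring degarelix |
|---|---|---|---|
| 0% | 90.5% | 90.5% | 2.5% |
| 1% | 90.6% | 88.0% | 3.4% |
| 2% | 90.7% | 85.2% | 4.4% |
| 5% | 91.1% | 74.3% | 9.4% |

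Equal rates barely change power. One-sided rates lose power or inflate the error, depending on the arm.

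**Inpatient mortality.** Let m be the all-cause death rate, equal in both arms, and let s be the share of deaths that occur before discharge. Inpatient mortality is m × s in each arm, so the difference, placebo minus degarelix, is m × (s_placebo − s_degarelix). If degarelix only brings discharge forward, s_degarelix is the smaller and the difference is positive, although survival is identical.

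**The case against.** Several stronger readings are tempting, and the documents do not support them.

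- **A reader might infer that the protocol deliberately counts dying patients as successes.** Hospice appears in neither document. The result follows from the wording, and the section 11 wording need not be met by a man dying of COVID-19 on an inpatient unit. What stands is that the section 2 rule is the one declared to govern the endpoints, and it has no exclusion.
- **A reader might fault every non-acute unit.** The rule turns on need for acute care, and counting a patient on a rehabilitation unit as discharged is reasonable.
- **A reader might conclude that deaths after discharge escape analysis.** They do not. Death anywhere by Day 15 fails the primary endpoint, death by Day 30 fails an alpha-controlled secondary endpoint, and SAP 3.7.5 analyses mortality to Day 60. The Day 30 composite mixes death with hospitalisation and ventilation, however, and the Day 60 analysis carries no alpha control.
- **A reader might size the problem from the cited 17% mortality**, for example 198 × 0.17 × an assumed hospice share. That 17% is two-week mortality under best supportive care in a severe-disease trial. This trial also admits patients not needing oxygen, and 132 of the 198 receive degarelix. Patients dead within two weeks already fail the primary endpoint, so the product says nothing about those alive on Day 15.

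The strongest objection is that the trial is double-blind and nothing in the documents suggests unequal transfer rates. That stands for the primary test. It does not answer the inpatient-mortality point, which needs only earlier discharge in one arm and no unblinding. It is also fair that the closing of that window at discharge is the ordinary meaning of the term and is not stated in the plan.

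**Conclusion.** The concern holds in this limited form. Applied as written, the discharge definition turns a live transfer to hospice or comfort care for COVID-19 into an irrevocable clinical improvement, a shorter stay and, for men alive and unventilated on Day 15, a primary non-failure. Inpatient mortality is undefined and, as ordinarily understood, can differ between arms without any difference in survival.

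The number of patients is unknown. Planned power is not threatened if transfer rates are similar (90.6% to 91.1% for an assumed 1% to 5% in both arms). Bias in the primary test requires imbalance: with no true effect and transfers in the degarelix arm only, the chance of a false result in its favour rises from 2.5% to between 3.4% and 9.4%. The main cost is to the interpretation of clinical improvement, length of stay and inpatient mortality. These figures use the plan's event rates and 0.05 level, and the range for h is an assumption.

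**What to change.** Settle the following before unblinding. It concerns scoring and data, not patient care.

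1. **Discharge definition.** State in Protocol section 2 and SAP 2.4 that, for endpoint scoring only, transfer or discharge to hospice or comfort care because of COVID-19 or its complications is not discharge. It counts as a failure on the Day 15 and Day 30 composites, is not a clinical-improvement event, and does not end the hospital stay as a favourable outcome; the SAP should say what value such a patient takes in the length-of-stay test. Leave the rehabilitation-unit rule unchanged. Record the discharge destination, align the section 11 wording, and point the SAP cross-reference to Protocol section 2.
2. **Mortality.** Test all-cause mortality through Day 30 in all randomised patients in place of inpatient mortality, with the same test and alpha of 0.0071. Report inpatient mortality descriptively. Vital status after discharge is already collected (footnote J; Form 18).
3. **Follow-up.** Reconcile SAP 2.3 with the 60-day follow-up in Protocol section 5 and SAP 3.7.5. Form 18 is first due at Day 30, so make sure the date of death is recorded; otherwise a death between discharge and Day 15 cannot be placed on the Day 15 composite.

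The cost is an amendment to a named secondary endpoint and one added data field. The sample size need not change: if the rule raises both failure rates by an assumed 1, 2 or 5 points, power with 62 and 124 patients stays at 90.4%.
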